2.8 Statistical Analyses for Primary and Secondary Outcomes

Analyses included patients in the groups to which they were assigned. Patients were censored at 24 months of follow-up or at the time of their last follow-up for patients lost to follow-up. The primary analysis was a proportional hazards model using a competing risk analysis (death as the competing risk) with time to the HEALTH primary study endpoint as the outcome. The independent variable was THA versus HA, and the following covariates were used: age (50-80 years or >80 years), pre-fracture living setting (institutionalized or not institutionalized), pre-fracture functional status (using aid or independent ambulator), and ASA Class (Class I/II or III/IV/V). For these covariates, we used values that were entered into the minimization system at time of enrollment. For our competing risk analyses, we used the method described by Zhou et al. to account for clustering within surgeons.⁶ The estimates from the competing risk analysis for clustered data analyses were marginal estimates. We report the treatment effects as hazard ratios (HRs) with 95% confidence intervals (CIs). No adjustment for multiplicity was made and the 95% CIs do not adjust for multiplicity. Kaplan-Meier curves were constructed for the primary outcome.

Cox proportional hazards modeling was used to estimate the relative effect of THA versus HA on time to mortality, serious adverse events, and hip-related complications, separately, and included the same independent variables as listed for the primary analysis as well as including surgeon as a random effect. The hip-related complications analysis was a competing risk analysis with death as the competing risk. The estimates from the competing risk analysis for clustered data analyses were marginal estimates. We report the HRs and 99% CIs for the proportional hazards models. We performed proportional hazards regressions only for hip-related complications in which there were at least 50 events. Using multi-level models, the effect of THA versus HA on quality of life (SF-12, EQ-5D), function (WOMAC), and mobility (TUG) were estimated separately. Randomized treatment, visit (entered as a categorical variable) were also included as independent variables. Because we believed that the effect of THA versus HA may change over time, we also included an interaction term between treatment and visit. When the interaction term between treatment and visit was not statistically significant at $\alpha=0.05$, we removed it from the model. When the interaction term was significant, we reported the treatment effect at each visit. We accounted for death via joint modelling, using the method described by Rizopoulos.⁷ The SF-12, WOMAC, and EQ-5D were summarized using mean difference (MD) and 99% CIs. We analyzed the TUG as a dichotomous outcome with the following categories: a) patients who complete the test in ≤ 12 seconds, and b) those who require >12 seconds to complete the test or were unable to complete the test. We selected 12 seconds as the cut-off because this was the threshold used by the Centers for Disease Control and Prevention.⁸ The TUG was summarized using odds ratios and 99% CIs. For our multi-level analyses of quality of life, function, and mobility, all available data were used with no imputation performed. The models do not require that a patient have valid scores at all follow-up visits. We chose alpha levels of 0.05 and 0.01 for the primary and secondary outcomes, respectively. When scoring the WOMAC domains, we used the mean of the items that were answered in our calculation if at least 4 of the 5 pain items were answered, at least 1 of the 2 stiffness items were answered, and if at least 14 of the 17 function items were answered. If there were less items answered, the domain was set to missing. To calculate the WOMAC total score, we required non-missing scores for all 3 domains.

When scoring the SF-12, we required at least half of each of the items in each domain to be answered to use the mean of the non-missing items as the domain score. The physical component summary score and the mental component summary score were only calculated if all 8 domains were non-missing.

All 5 questions of the EQ-5D were required to calculate the utility score.

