### 1.1 Background

Hip fractures occur in 280,000 Americans (over 5,000 per week) and 36,000 Canadians (over 690 per week) annually (Cummings et al, 1990). By the year 2040, the number of people aged 65 or older will increase from 34.8 million to 77.2 million (U.S. Bureau of the Census, 1998). Demographic projections by Statistics Canada indicate that by the year 2041, 1 in 4 Canadians will be over the age of 65 years (Statistics Canada, 1994). The number of hip fractures is likely to exceed 500,000 annually in the United States and 88,000 in Canada over the next 40 years (Johnell et al, 2004; Cooper et al, 1992; Cummings et al, 1990). By the year 2040, the estimated annual health care costs will reach \$9.8 billion in the United States and \$650 million in Canada (Papadimitropoulos et al, 1997).

Hip fractures are associated with a 30% mortality rate at 1 year (Moran et al, 2005) and profound temporary, and sometimes permanent, impairment of independence and quality of life (Jongjit et al, 2003; Wilkins et al, 1999). Worldwide, 4.5 million persons are disabled from hip fractures yearly with an expected increase to 21 million persons living with disability in the next 40 years (Johnell et al, 2004; Cooper et al, 1992; Cummings et al, 1990). Hip fractures account for more hospital days than any other musculoskeletal injury and represent more than two thirds of all hospital days due to fractures (AAOS, 1999). Length of hospital stays in Canada is estimated at 465,000 patient-days annually with a projected increase to 1.8 million days annually by 2040 (Papadimitropoulos et al, 1997). The disability adjusted life-years lost as a result of hip fractures ranks in the top 10 of all cause disability globally (Cooper et al, 1992).

Hip Fractures are anatomically classified in relation to the hip capsule as intracapsular fractures (i.e., femoral neck) or extracapsular fractures (i.e., inter-trochanteric and sub-trochanteric) (**Figure 1**). This trial focuses on the management of displaced fractures of the femoral neck.

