## **2. STUDY OBJECTIVES**

### **2.1 Primary Objective**

The primary objective is to assess the impact of total hip arthroplasty versus hemi-arthroplasty (i.e., bipolar or modular unipolar) on rates of secondary procedures at 2 years in individuals with displaced femoral neck fractures.

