Based upon aggregate data from the pilot study, annual mortality rates of 15% and a loss to follow-up of 5% in each group were assumed, these rates applying to each of the two years of follow-up. Informed by the meta-analysis, the following assumptions were made: a one year risk of having a secondary procedure of 5% in the HA group and a risk of 1% in the second year. Various values of the relative risk reduction (HA vs. THA) were then used to identify the specific value that would correspond to a cumulative risk difference between THA and HA of 5% after 2 years. This figure was identified in a survey of participating surgeons as the minimally important difference to clinicians. Annual event risks by group were converted into equivalent hazard rates, assuming for simplicity that the hazard rate would be approximately constant within each of the two years. It is estimated that approximately 72% of the group receiving THA and 76% of the group receiving HA will be event-free and available for further follow-up at the start of the second year. The sample size was increased to allow for a combined 7.6% crossover rate from the assigned to the alternate treatment, based on pilot data. These assumptions lead to a required total sample size of 1,316 patients, which will yield an expected number of 96 secondary procedures. The associated relative risk reduction (RRR) is 0.45.

These calculations were repeated after replacing the 5% event risk at one year for HA by 4% and 6% and leaving the other factors unchanged (**Table 3b**). To account for potential surgeon level effects, the sample size has been further increased by 9% to 1,434.

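### SAP 2.8 models the primary outcome with death as a competing risk but plots Kaplan-Meier curves; if deaths are censored in them, 2-year absolute risks read about 11% too high in relative terms at the planning inputs

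*SAP*

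**What the plan says.** Protocol 2.1 sets the primary objective as the effect of THA versus HA "on rates of secondary procedures at 2 years in individuals with displaced femoral neck fractures".

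For that outcome, SAP 2.8 states: "The primary analysis was a proportional hazards model using a competing risk analysis (death as the competing risk"). Its censoring rule reads: "Patients were censored at 24 months of follow-up or at the time of their last follow-up for patients lost to follow-up". Death is not mentioned there. The paragraph closes with the display: "Kaplan-Meier curves were constructed for the primary outcome". No cumulative incidence curve is named in SAP 2.8 or elsewhere in the text available for review.

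Protocol 7.2.1 had planned a Cox model with Kaplan-Meier curves. The SAP changed the model to a competing-risk analysis and kept the curves.

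On the expected frequency of death, protocol 7.1 says that "annual mortality rates of 15% and a loss to follow-up of 5% in each group were assumed", in each of the two years.

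**The concern.** The model and the figure for the same outcome appear to rest on different treatments of death. A competing-risk model recognises that a patient who has died can no longer have a secondary procedure. A Kaplan-Meier curve with deaths censored assumes that such a patient keeps the same future risk as those still alive. One minus that curve is then larger than the probability of having a procedure by a given time whenever some deaths precede events that others go on to have. At 15% mortality a year, deaths in this trial are expected to outnumber events.

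What is at stake is the absolute scale. SAP 2.8 reports the primary outcome as a hazard ratio, so the curve is the only absolute-risk display that section names. Protocol 7.1 also defines the minimally important difference in absolute terms, as 5 percentage points cumulative at 2 years. A reader who takes 2-year risks, or their difference, from the curves would get values that are too high.

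**Working it through.** **Inputs (protocol 7.1).** "a one year risk of having a secondary procedure of 5% in the HA group and a risk of 1% in the second year"; relative risk reduction 0.45 (HA vs THA); mortality 15% and loss to follow-up 5% per year in each arm; hazards constant within each year. The THA annual risks are 0.05/0.55 = 9.09% and 0.01/0.55 = 1.82%.

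**Step 1: reproduce the protocol's own figure.** Each annual risk p becomes a hazard h = -ln(1 - p). Expected events per patient are the sum over the two years of S × h/(h + h_d + h_l) × [1 - exp(-(h + h_d + h_l))]. Here h_d and h_l are the hazards of death and loss, and S is the proportion event-free and in follow-up at the start of the year.

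- HA: 0.0520; THA: 0.0940.
- With 658 patients per arm (1,316/2): 34.2 + 61.9 = 96.05 events. The protocol states 96.
- Event-free and available at the start of year 2: HA 76.7%, THA 73.4%. The protocol states about 76% and 72%.

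The hazard method therefore matches the one in the protocol.

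**Step 2: the two curves at 24 months.** Loss to follow-up is treated as independent censoring and drops out of both estimands.

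One minus Kaplan-Meier, deaths censored, is 1 - (1 - p1)(1 - p2):
- HA: 1 - 0.95 × 0.99 = 5.95%
- THA: 1 - 0.9091 × 0.9818 = 10.74%

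Cumulative incidence is the Step 1 sum with event and death hazards only (h_d = -ln 0.85 = 0.1625):
- HA year 1: 0.0513/0.2138 × (1 - 0.8075) = 0.0462. Year 2: 0.8075 × 0.01005/0.1726 × (1 - 0.8415) = 0.0075. Total 5.36%.
- THA year 1: 0.0953/0.2578 × (1 - 0.7727) = 0.0840. Year 2: 0.7727 × 0.01835/0.1809 × (1 - 0.8345) = 0.0130. Total 9.70%.

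The excess, from unrounded values, is 0.59 points for HA (10.9% relative) and 1.05 points for THA (10.8% relative). The THA minus HA difference is 4.79 points on Kaplan-Meier and 4.34 points on cumulative incidence.

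At 12 months the figures are HA 5.00% vs 4.62% and THA 9.09% vs 8.40%, about 8% relative.

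**Step 3: other inputs, 24 months.** The first three rows are those of protocol Table 3b, all at 15% mortality. The rest use the 5% row.

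| Setting | HA: 1-KM vs CIF | THA: 1-KM vs CIF | Relative excess |
|---|---|---|---|
| HA 4%, RRR 0.50 | 4.96% vs 4.45% | 9.84% vs 8.84% | 11.4-11.5% |
| HA 5%, RRR 0.45 | 5.95% vs 5.36% | 10.74% vs 9.70% | 10.8-10.9% |
| HA 6%, RRR 0.42 | 6.94% vs 6.28% | 11.89% vs 10.78% | 10.4-10.5% |
| Mortality 10% a year | 5.95% vs 5.56% | 10.74% vs 10.05% | about 7% |
| Mortality 20% a year | 5.95% vs 5.17% | 10.74% vs 9.35% | about 15% |
| Mortality 30% a year | 5.95% vs 4.77% | 10.74% vs 8.64% | 24-25% |
| Mortality 30%, then 15% | 5.95% vs 4.83% | 10.74% vs 8.74% | about 23% |

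The last row takes its first-year value from protocol 1.1: "Hip fractures are associated with a 30% mortality rate at 1 year".

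**Step 4: timing of events (an assumption, not in the documents).** At 15% mortality, if all year-1 events fall in the first 3 months, the excess is 0.30 points for HA and 0.54 for THA, or 5.2% to 5.4% relative.

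**Step 5: relative effect.** The ratio ln(1 - F_THA)/ln(1 - F_HA) at 24 months is 1.853 on Kaplan-Meier and 1.851 on cumulative incidence. With equal mortality in the arms, the relative effect is practically unchanged.

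**The case against.** The strongest objection is that the defect is inferred. The censoring rule lists two reasons, and death is not one of them. If patients who died were kept in the risk set to 24 months, the bias would largely vanish. This stands as a limit, and it is why the conclusion is conditional. It does not remove the point: Kaplan-Meier as ordinarily built censors deaths, and the SAP says nothing to show that its curves were built otherwise.

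Second, no reported result is shown to be wrong. SAP 2.8 reports hazard ratios and does not say that risks are read from the curves. SAP 2.11 uses the curve for the time pattern of the effect, which is relative. That is correct, and it confines the point to absolute risks.

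Third, SAP 2.10(e) specifies analyses of proportions, so another absolute-scale analysis exists. It is a sensitivity analysis for loss to follow-up, does not say how deaths are counted, and does not correct the curves.

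Fourth, the 11% depends on hazards being flat within each year, which the protocol adopts for simplicity. Putting 80% of the year-1 event hazard in the first 3 months gives 6.6% to 6.8%; if half of the year-1 death hazard also falls there, 8.5% to 8.7%. So 11% is the figure at the planning inputs and not a central value over timing. The direction does not change.

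Fifth, the 30% mortality in protocol 1.1 describes hip fractures in general. The trial requires prior ambulation and excludes frank dementia, and its 15% comes from pilot data. The 23% to 25% figures are therefore an upper sensitivity range and not planning values.

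Finally, some SAP pages were not in the text available for review, so the absence of a cumulative incidence curve is confirmed only for the rest.

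**Conclusion.** The concern holds. SAP 2.8 accounts for death in the primary model but names a display that, as usually constructed, does not. If deaths are censored in the curves, the 2-year risks they show are too high by about 0.6 points for HA and 1.0 points for THA at the planning inputs, about 11% in relative terms. The risk difference is inflated by about 0.45 points, against the protocol's 5-point benchmark.

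These sizes assume equal 15% annual mortality in both arms and constant hazards within each year. Early clustering of events reduces them to roughly 5% to 7%; higher mortality raises them. The primary inference is untouched. This should be corrected, but it does not call the trial's main conclusion into question.

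**What to change.** In SAP 2.8, replace the Kaplan-Meier curves for the primary outcome with Aalen-Johansen cumulative incidence curves by arm, with death as the competing event. Take any 12- and 24-month absolute risks and risk differences, with confidence intervals, from those curves. State how deaths are handled in every curve shown, and label any Kaplan-Meier curve that is kept as censoring deaths.

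The cost is almost nil: a change of estimator and a label for one figure, from data already collected.

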## **1.5 Alternative Operative Management Strategies in Femoral Neck Fractures – Direct Comparisons for Randomized Trials**

A comprehensive literature search to identify all studies relevant to the relative merits of hemi-arthroplasty versus total hip arthroplasty for displaced femoral neck fractures identified 4 randomized controlled trials (RCTs) comparing internal fixation, hemi-arthroplasty, and total hip arthroplasty. Of these, 1 trial was an updated publication of an earlier study, and another reported only aggregate results for all arthroplasty. Thus, 2 randomized trials (Ravikumar et al, 2002; Keating et al, 2005) provided sufficient detail for statistical pooling of results. Current

best estimates of treatment effect suggest that total hip arthroplasty reduces hip pain (RRR=0.24, 95% CI: 2%-41%), and may reduce functional limitations (RRR=0.10, 95% CI: 24%-26%), when compared with hemi-arthroplasty. The reduction in pain and improvement in function may come at the cost of an increased risk of hip dislocation (RR=2.95%, 95% CI: 0.40-21.74). Despite the trend toward an increase in hip dislocation, the data (point estimate) show a trend toward decrease in secondary procedure rates with hemi-arthroplasty, although the sparse data is associated with very wide confidence intervals (RRR=0.14, 95% CI: 53%-59%). In addition to the small sample sizes, these trials are limited by lack of concealed randomization in 1 trial (Ravikumar et al, 2002), and a differential expertise bias (Devereaux et al, 2005), as more experienced surgeons usually conducted the total joint arthroplasty than the hemi-arthroplasty (Keating et al, 2005).

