### **1.6 Hemi-Arthroplasty versus Total Hip Arthroplasty – Indirect Comparisons from Meta-Analyses**

Two meta-analyses (Lu-Yao et al, 1994; Bhandari et al, 2003) were identified that provided indirect comparisons of total hip arthroplasty and hemi-arthroplasty. Lu-Yao pooled observational studies and randomized trials of total hip arthroplasty (N=746 patients) versus hemi-arthroplasty (N=4,530 patients), and found reductions in the risk of secondary procedures, mortality, wound infection, and hip pain with total hip arthroplasty. Bhandari's meta-analysis restricted to randomized trials (N=662 patients) suggested similar rates of secondary procedures, decreased mortality, decreased infection rates, and large benefits in patient function with total hip arthroplasty. Both meta-analyses reported at least 2-fold higher hip dislocation rates with total hip arthroplasty.

In summary, both direct and indirect evidence suggests substantial benefit of total hip arthroplasty over hemi-arthroplasty in decreased pain and improved function. Both direct and indirect evidence suggest increased rates of dislocation with total hip arthroplasty. Despite this increased dislocation rate, indirect evidence suggests similar secondary procedure and mortality rates with the 2 procedures. While direct evidence is consistent with similar rates of secondary procedures and mortality, the data from direct comparisons are so sparse as to be uninformative.

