### **2.2 Secondary Objectives**

Secondary objectives are:

1. To examine the effect of total hip arthroplasty versus hemi-arthroplasty on health-related quality of life (Short Form-12, SF-12), functional outcomes and mobility (Western Ontario McMaster Osteoarthritis Index, WOMAC, and Timed Up and Go Test, TUG), and health outcome measures (EuroQol-5 Dimensions, EQ-5D).
2. To evaluate the effect of total hip arthroplasty versus hemi-arthroplasty on mortality.
3. To evaluate the effect of total hip arthroplasty versus hemi-arthroplasty on hip-related complications including:
  - Peri-prosthetic fracture
  - Hip instability or dislocation
  - Implant failure (loosening/subsidence and breakage)
  - Wound healing problems (including superficial/deep infection, wound necrosis)
  - Soft tissue problems (i.e. pseudotumor)
  - Heterotopic ossification
  - Abductor failure
  - Implant wear and corrosion
  - Osteolysis
  - Neurovascular injury
  - Decreased function
  - Pain

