### 3.2.2 Secondary Outcomes

Secondary outcomes will include:

Functional outcome and quality of life will be measured using self-administered and interview-administered questionnaires. Functional outcome questionnaires will include a generic health status measurement instrument (SF-12), a hip function and pain questionnaire (WOMAC), a health outcome measure (EQ-5D), and a functional mobility test (TUG). HEALTH will further report the effect of total hip arthroplasty versus hemi-arthroplasty on mortality and hip-related complications including:

- Peri-prosthetic fracture
- Hip instability or dislocation
- Implant failure (loosening/subsidence and breakage)
- Wound healing problems (including superficial/deep infection, wound necrosis)
- Soft tissue problems (i.e. pseudotumor)
- Heterotopic ossification
- Abductor failure
- Implant wear and corrosion
- Osteolysis
- Neurovascular injury
- Decreased function
- Pain

At 1 week, 10 weeks, 6 months, 12 months, and 24 months after surgery the research coordinator or nurse will ascertain patient status via clinic visits and completion of self-administered quality of life forms (SF-12, WOMAC, and EQ-5D) and the functional mobility test (TUG) (**Figure 7**). During all visits the research coordinator or nurse should be prepared to conduct interview-administered data collection if patients are unable to complete the self-administered forms. Hip-related complications will also be documented at each follow-up. Other serious adverse events and non-hip related complications will also be recorded (refer to section 9.0). At 9 months and 18 months after surgery the research coordinator or nurse will ascertain patient status (i.e., secondary procedures, hip-related complications, deaths), as well as administer quality of life questionnaires (SF-12, WOMAC, and EQ-5D) via telephone calls and verifying information in medical records.

The **SF-12** questionnaire was developed from the Medical Outcomes Study (McHorney et al, 1992). It is a self-administered, 12-item questionnaire that measures health-related quality of life in 8 domains. Both physical and mental summary scores can be obtained. Each domain is scored separately from 0 (lowest level) to 100 (highest level) (Ware et al, 1996).

The **WOMAC** index is self-administered and assesses the three dimensions of pain, disability and joint stiffness in knee and hip osteoarthritis using a battery of 24 questions (Bellamy et al, 1988).

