2.6 Outcome Definitions

Primary Outcome

| Outcome | Definition |
|---|---|
| Unplanned Secondary Hip Procedure (study event) | Unplanned secondary procedures that were classified as study events included: 
 ○ Closed reduction of hip dislocation ○ Open reduction of hip dislocation ○ Open reduction of fracture ○ Soft tissue procedure ○ Insertion of antibiotic spacer ○ Full implant exchange ○ Partial implant exchange – stem only ○ Partial implant exchange - head only ○ Partial implant exchange - liner only |

| Outcome | Definition |
|--|---|
| | 
 ○ Partial implant exchange - head and liner ○ Partial implant exchange – acetabular component only ○ Partial implant exchange – acetabular component and head ○ Implant adjustment – re-orientation of the stem ○ Implant adjustment – re-orientation of the acetabulum component ○ Implant removal with no replacement ○ Excision heterotopic ossification ○ Supplementary fixation ○ Other |
| Reason for Unplanned Secondary Procedure | 
Classification of the reason for unplanned secondary procedures included:
 
 ○ Treat a peri-prosthetic fracture ○ Treat hip instability or dislocation ○ Treat infection – superficial ○ Treat infection – deep ○ Treat wound necrosis ○ Treat another wound healing problem ○ Remove heterotopic ossification ○ Manage abductor failure ○ Manage another soft tissue problem (i.e. pseudotumor) ○ Correct implant failure –loosening or subsidence ○ Correct implant failure - breakage ○ Treat implant wear ○ Treat osteolysis ○ Treat implant corrosion ○ Improve function ○ Relieve pain |

Secondary Outcomes

| Outcome | Definition |
|--------------------------|---|
| Mortality | Mortality was adjudicated by the Central Adjudication Committee and it was considered to be an event if it occurred within 24-months of the initial hip fracture surgery. |
| Serious Adverse Events | Serious adverse events, as diagnosed by physicians at the clinical sites, were documented. A serious adverse event was defined as any adverse event that is fatal, life threatening, requires or prolongs hospital stay, results in persistent or significant disability or incapacity, a congenital anomaly or birth defect, or an important medical event, symptom, sign, illness, or experience that develops or worsens in severity during the study. |

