The Central Adjudication Committee adjudicated adverse events related to the patient's randomized hip as reported by the clinical site after each participant had completed their 24-month follow-up (or following early withdrawal). The Central Adjudication Committee also reviewed all available x-rays (scheduled visits and unscheduled visits) to look for radiographic evidence of hip-related complications that were not reported by the clinical site. The Central Adjudication Committee was responsible for determining when the hip-related adverse event was first diagnosed/evident on participant x-rays. Hip-related complications that were considered study events included:

- f) Peri-prosthetic fracture
- g) Hip instability or dislocation
- h) Implant failure (loosening/subsidence and breakage)
- i) Wound healing problems (including superficial/deep infection, wound necrosis)
- j) Soft tissue problems (i.e. pseudotumor)
- k) Heterotopic ossification
- l) Abductor failure
- m) Implant wear and corrosion
- n) Osteolysis
- o) Neurovascular injury
- p) Decreased function
- q) Pain

The Chair of the Central Adjudication Committee independently reviewed all cases of heterotopic ossification that were identified by the Central Adjudication Committee. For each participant that was identified as having radiographic evidence of heterotopic ossification, the Chair independently reviewed the x-rays from each post-operative assessment and determined the severity of heterotopic ossification using the classification system developed by Brooker and colleagues:

- Stage I: Islands of bone within soft tissues of any size of the hip
- Stage II: Bone spurs from pelvis or femur, leaving at least 1 cm between opposing bone surfaces
- Stage III: Bone spurs from pelvis or femur reducing the space between opposing bone surfaces to less than 1 cm
- Stage IV: Ankylosis of the hip

The Central Adjudication Committee reviewed all available x-rays, and data from the patient's completed case report forms.

5) Mortality

The Central Adjudication Committee adjudicated mortality as required following a patient's early withdrawal. The Central Adjudication Committee reviewed all data from the patient's completed case report forms, available clinical notes, and/or x-rays to confirm the cause of death. They also commented on the relation to the treatment arm.

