2.11 Interpretation of Blinded Data

Hypothesis: We hypothesize that THA will have similar or lower rates of secondary procedures and higher functional outcome scores at 24 months compared with HA.

Here, we present alternative interpretations of blinded preliminary results. Blinded data interpretation may decrease the frequency of misleading data interpretation. Widespread adoption of blinded data interpretation with a minimum set of recommendations should be widely adopted.¹⁰

Secondary procedures over two years did not differ between treatment groups X and Y. The Kaplan Meier curve for the primary outcome suggests that the hazard ratios (HRs) remain constant up to 1 year (HR=1.30, 95% CI 0.86-1.95, $p=0.217$; non-significant estimates favoring treatment Y) and suggested estimates favouring treatment X after 1 year (up to 2 years) (HR=0.24, 95% CI 0.08-0.73; $p=0.011$).

Deaths did not differ between treatment groups X and Y over a 2-year period ($p=0.493$).

Serious adverse events ($p=0.052$) and hip-related complications ($p=0.277$) between treatment groups X and Y did not differ over a 2-year period.

Treatment X demonstrated significantly better overall WOMAC and EQ-5D utility scores ($p<0.05$) compared to Treatment Y (and trended towards better SF-12 PCS scores) over a 2-year period. TUG scores (cut-off 12 seconds) did not differ between treatment groups ($p=0.181$).

Subgroup analyses did not show any differences in the treatment effect between different subgroups ($p>0.05$).

Given the above preliminary findings, the more plausible hypothesis follows. Treatment X is THA and Treatment Y is HA. THA does not result in a statistically significant difference in secondary procedure rates over a 2-year period compared to HA; however, our findings suggest THA may have more secondary procedures earlier (less than 1 year, possibly driven by higher dislocations *results still blinded*) and HA may have more secondary procedures after 1-year post-fracture in those who did not have a secondary procedure during the first year. Functional outcome scores over 2 years favour THA compared to HA. These differences in function are small (although statistically significant). A lack of difference in secondary procedures, hip-related complications, and deaths, a lack of subgroup effects, and modest improvements in function render THA mildly superior to HA over 2 years. It's not unreasonable to consider the two treatments similar given

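### Below 50 events, SAP 2.8 plans no between-arm estimate for hip dislocation, the harm the protocol expects from total hip arthroplasty; an unadjusted estimate should be added

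*SAP*

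**What the plan says.** The analysis rule is in SAP 2.8. Time to mortality, serious adverse events and hip-related complications are modelled separately, with four baseline covariates, allowance for surgeon, and 99% confidence intervals. Death is the competing risk for complications. The rule then adds: "We performed proportional hazards regressions only for hip-related complications in which there were at least 50 events". It makes no exception for any complication and gives no alternative measure below the limit.

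The protocol is broader. Section 2.2 lists "Hip instability or dislocation" among the complications to be evaluated as a secondary objective. Section 3.2.2 states: "HEALTH will further report the effect of total hip arthroplasty versus hemi-arthroplasty on mortality and hip-related complications including", and dislocation is on the list that follows. Section 7.2.2 plans Cox hazard ratios with 95% intervals and Kaplan-Meier curves for hip-related complications, with no minimum count.

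The protocol also says why dislocation matters. Section 1.5 says of THA: "The reduction in pain and improvement in function may come at the cost of an increased risk of hip dislocation", with a relative risk of 2.95 and a very wide 95% CI of 0.40 to 21.74. Section 1.6 adds: "Both meta-analyses reported at least 2-fold higher hip dislocation rates with total hip arthroplasty".

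**The concern.** Dislocation is the main anticipated cost of THA, to be weighed against less pain and better function. A plan that models it only when events reach 50 leaves the result for that harm dependent on a count that nobody controls. Below 50, a reader may see numbers by arm, but the available text commits to no risk difference, risk ratio, cumulative incidence or interval.

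The composites are not a substitute. The complication list in SAP 2.7 also contains pain and "Decreased function", which may favour THA on the protocol's own evidence. Dislocations treated by closed or open reduction enter the primary outcome together with many other procedures. A dislocation counts as a serious adverse event only if it meets that definition, for example if it "requires or prolongs hospital stay".

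The gap has a practical side. SAP 2.11, in its blinded reading, suggests that early secondary procedures are "possibly driven by higher dislocations" in the THA arm. A reader would want a dislocation estimate to check that remark.

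**Working it through.** **Inputs from the documents.** The threshold is 50 events (SAP 2.8). The secondary alpha is 0.01 with 99% intervals (SAP 2.8), and tests are two-sided (Protocol 7.1). The total sample is 1,434 (Protocol 7.1), which reproduces as 1,316 × 1.09 = 1,434.4. The plan gives no calculation behind the figure of 50, so there is nothing further of its own to reproduce.

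**Assumptions.** Arms are equal: 1,434 / 2 = 717. The documents give no dislocation rate, so the 24-month risks are assumed over a range. THA:HA ratios are 2 (Protocol 1.6) and 2.95 (Protocol 1.5). Counts are binomial within each arm.

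**Step 1: what 50 events means.** 50 / 1,434 = 3.5% overall. An expected count of 50 needs an HA risk of 50 / (717 × 3) = 2.3% at ratio 2 (THA 4.6%), or 50 / (717 × 3.95) = 1.8% at ratio 2.95 (THA 5.2%).

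**Step 2: chance of falling below 50.** Expected events = 717 × (HA risk + THA risk). The probability is the exact distribution of the sum of the two binomials.

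| HA vs THA risk | Expected events | P(fewer than 50) |
|---|---|---|
| 1% vs 2.95% | 28.3 | over 99% |
| 1.5% vs 3% | 32.3 | over 99% |
| 1.5% vs 4.4% | 42.5 | 86% |
| 2% vs 4% | 43.0 | 84% |
| 2.5% vs 5% | 53.8 | 28% |
| 2% vs 5.9% | 56.6 | 17% |
| 3% vs 6% | 64.5 | 2% |

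The result swings from near certainty to near zero over a narrow band of risks.

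**Step 3: is there information below 50?** Take 49 events, the most that would get no model, split 12 (HA) vs 37 (THA).

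- Risk ratio = 37 / 12 = 3.08.
- SE of its log = √(1/12 + 1/37 − 2/717) = 0.328.
- 99% CI = 3.08 ÷ and × exp(2.576 × 0.328), which is 1.32 to 7.18.
- Risk difference = 25 / 717 = 3.49 points. Its SE is √[(0.0167 × 0.9833 + 0.0516 × 0.9484) / 717] = 0.955 points, so the 99% CI is 1.03 to 5.95.

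**Step 4: allow for surgeons.** Protocol 7.1 raises the sample by 9% for surgeon effects. Treating that as a design effect of 1.09 (an assumption), the SE becomes 0.328 × √1.09 = 0.342 and the risk ratio interval is about 1.28 to 7.45. It still excludes 1.

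**Step 5: the weak end.** At 1% vs 2% the expected counts are 7.17 and 14.34, about 22 events. The risk ratio is 2.0 and SE = √(1/7.17 + 1/14.34 − 2/717) = 0.454, so the 99% CI is 0.62 to 6.45. That is wide, but it still shows which effects the data do not exclude.

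**The case against.** A minimum count for a regression is sensible. The model has treatment plus four covariates, so 50 events is ten per term before any allowance for surgeon clustering. The SAP does not give this reason, but it is a fair inference, and the minimum should stay for that model.

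The gap is also conditional. At 50 or more dislocations a hazard ratio with a 99% interval is planned. The sentence restricts regressions, not reporting. Dislocation is adjudicated as its own item, and anyone with counts and arm sizes could compute a ratio. That stands, but no sentence in the available text promises even those counts, and a prespecified estimate is better than one left to the reader.

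The SAP text available starts at section 2.0, so a table of complications by arm may exist elsewhere. The point is limited to what can be read.

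Several stronger readings are not supported:

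- **That the rule drops dislocation from the results.** It does not bar counts, and it does not apply at 50 or more events.
- **That the rule is likely to bite.** Step 2 shows that this depends on a rate the documents do not give.
- **That any excess just under 50 events would be clear-cut.** A split of 15 vs 34 gives a risk ratio of 2.27 (99% CI 1.03 to 4.98), but with the same assumed design effect the interval is 0.997 to 5.15.
- **That the overall complications result is sure to be available whatever its count, or that it masks dislocation.** SAP 2.8 does not state the first, and how far opposing effects offset is unknown.
- **That the readings in SAP 2.11 are wrong.** They are narrative interpretations made while blinded, not a decision rule.

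**Conclusion.** The concern holds as a conditional gap. SAP 2.8 introduces a limit that Protocol 7.2.2 does not have. If fewer than 50 dislocations occur, the available text leaves this named harm with no planned effect estimate or interval of its own. The protocol evidence for an excess is consistent in direction, although the direct estimate is very imprecise.

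The chance that the gap opens runs from 2% to over 99% across the assumed risks and cannot be narrowed from the documents. The example with 49 events shows that useful estimates exist below the limit. It rests on equal arms and, for the wider interval, on a design effect of 1.09. The primary outcome, its alpha and its analysis are unaffected. This is a minor point and a cheap improvement.

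**What to change.** Change SAP 2.8 only. Keep the 50-event sentence, state that it governs the adjusted clustered model, and add:

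*Dislocation (including instability) is compared between randomised arms whatever the number of events. Counts, 24-month cumulative incidence with death as competing risk, and the risk difference and risk ratio with 99% confidence intervals are reported, preferably with standard errors robust to clustering by surgeon.*

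The cost is two sentences and one table row, using data that are already adjudicated. The downsides are a wide interval if events are few (Step 5) and an estimate not adjusted for the minimisation factors. SAP 2.11 should stay as it is: it records a reading made while blinded, and editing it would change no analysis.
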